6. DATA SETS ANALYZED (STUDY POPULATIONS)

The analysis sets are defined as follows.

6.1. Intent to Treat Set

The Intent-to-treat (ITT) Set will include all randomized participants.

The ITT Set was used for disposition summaries.

6.2. Modified Intent-to-Treat Set

The Modified Intent-to-Treat (mITT) Set will include all randomized participants, excluding participants who enrolled prior to the availability of Shiga toxin-related hemolytic uremic syndrome (ST-HUS) and a disintegrin and metalloproteinase with a thrombospondin type 1 motif, member 13 (ADAMTS13) central laboratory results and are subsequently found to be ineligible after randomization.

The mITT Set was selected as the primary efficacy population to ensure the exclusion of participants with thrombotic thrombocytopenic purpura (TTP) or ST-HUS as potential confounders in the efficacy analyses, as these conditions present similarly to the target population but have distinct clinical prognosis and management. For the efficacy assessments, participants will be assessed according to the treatment they were randomized to receive, regardless of the treatment they actually received ("as randomized" approach).

6.3. Per-Protocol Set

The Per-Protocol Set (PPS) will consist of mITT participants who met all of the following criteria. The primary analysis will be repeated on the PPS as supplementary analyses. PPS will be analyzed according to the participants' randomized treatment assignment.

- 1. Participants who received full randomized intervention during the 26-week randomized Treatment Period
- 2. Did not receive any disallowed medications or undergo any disallowed therapeutic procedures as described in Protocol Section 6.6.2:
 - Experimental interventions or therapies
 - Eculizumab or other agents that act on the complement pathway
 - Therapeutic plasma exchange/plasma infusion following randomization
- 3. Met inclusion criteria (IC) in the study:
 - IC 4: TMA within ≤ 14 days prior to Screening is associated with at least one of the following triggers:
 - a) Autoimmune (lupus nephritis or systemic sclerosis-associated TMA [SSc-TMA])
 - b) Infection
 - c) Solid organ transplant (eg, kidney, pancreas, liver, heart, or small bowel)
 - d) Drugs
 - e) Malignant hypertension

- IC 5: Confirmation of all of the following laboratory findings during the Screening Period and/or ≤ 14 days prior to the start of the Screening Period:
 - a) Platelet count $< 150,000/\mu$ L
 - b) $LDH \ge 1.5 \times upper limit of normal and hemoglobin \le LLN (based on age and sex)$
 - c) Acute kidney injury as defined by meeting 1 or more of the following criteria (for kidney transplant recipients, the pre-TMA value is based on post-transplant eGFR):
 - Acute decline in eGFR \geq 50% from pre-TMA value (the pre-TMA value must be \leq 12 months prior to Screening)
 - New acute kidney injury with an eGFR \leq 30 mL/min/1.73 m²
 - New initiation of dialysis due to TMA requiring > 1 session and for no more than 14 days prior to Screening
- 4. Did not violate important exclusion criteria (EC) in the study, including the following:
 - EC 1: Any known gene mutation that causes aHUS
 - EC 3: Known chronic kidney disease (CKD):
 - In participants with native kidneys: $eGFR \le 45 \text{ mL/min}/1.73 \text{ m}^2$ by the CKD-Epidemiology Collaboration (CKD-Epi) equation (Levey, 2009) due to any cause or ongoing acute kidney injury requiring dialysis treatment lasting for > 14 days prior to Screening.
 - In kidney transplant recipients: determination of the CKD threshold will be based on Investigator judgment.
 - EC 5: Primary and secondary glomerular diseases other than lupus
 - EC 6: Diagnosis of primary antiphospholipid antibody syndrome
 - EC 7: Shiga toxin-producing *E coli* infections, including, but not limited to, ST-HUS
 - EC 8: Known familial or acquired ADAMTS13 deficiency (activity < 5%)
 - EC 9: Positive direct Coombs test result, which, in the judgement of the Investigator, is indicative of a clinically significant immune-mediated hemolysis not due to TMA
 - EC 10: Clinical diagnosis of disseminated intravascular coagulation in the judgment of the Investigator, utilizing the International Society on Thrombosis and Haemostasis scoring criteria
 - EC 11: Presence of sepsis requiring vasopressors within 7 days prior to or during Screening
 - EC 13: Known bone marrow insufficiency or failure as evidenced by cytopenias
 - EC 14: Kidney biopsy (if available) showing any of the following in glomeruli:
 - $\circ \geq 50\%$ interstitial fibrosis tubular atrophy
 - $\circ \geq 50\%$ glomerulosclerosis

- $\circ \geq 50\%$ crescent formation
- EC 22: Respiratory failure from any cause requiring mechanical ventilation (including intubation, bilevel positive airway pressure, or continuous positive airway pressure) within 72 hours prior to randomization
- EC 23: Use of any complement inhibitors within the past 3 years
- EC 24: Participation in the following types of interventional treatment studies within 30 days before Day 1 in this study or within 5 half-lives of that investigational treatment, whichever is greater:
 - Interventional treatment study of any unapproved therapy regardless of indication
 - Interventional treatment study of any therapy (approved or unapproved) being evaluated for TMA intervention

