### **6.6.2. Disallowed Medicine and Therapy**

Participants are prohibited from receiving therapeutic plasma exchange/plasma infusion at any time following randomization during the Treatment Period. Participants are prohibited from receiving any of the following medications and therapies during the entire duration of study participation:

- Experimental interventions or therapies
- Eculizumab or other agents that act on the complement pathway

In the event that a participant receives a prohibited medication and/or therapy, the Investigator must confer with the Medical Monitor to determine if the participant should discontinue study drug (Section [7.1](#)).

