Participants will be classified as nonresponders if they do not have any TMA response observed before the following intercurrent events: treatment discontinuation or start of disallowed therapy or medicine, regardless of whether the TMA response is observed after these intercurrent events. For other participants without the above intercurrent events, whether the TMA response occurs by 26 weeks will be assessed using all available assessments within the 26-week randomized Treatment Period.

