7.1.1. Handling Missing Data

For binary endpoints, a nonresponder imputation (NRI) method will be used by categorizing any participants who have a missing value for categorical variables at a specific visit as a nonresponder for that visit. In addition, participants who have the following intercurrent events will be assigned as nonresponders, regardless of whether any response is observed after these intercurrent events: premature discontinuation of the study treatment or initiation of disallowed therapy or medicine, before observing the response for an endpoint in analysis.

For time-to-event endpoints (time to complete TMA response, time to response for each individual TMA parameter), missing data and data after intercurrent events of premature discontinuation of study treatment or initiation of disallowed therapy or medicine will be censored.

For the continuous secondary endpoint, no missing data handling will be performed. Summary statistics will be provided using observed data.

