7.2.2. Protocol Deviations

Protocol deviations will be determined per the standard operating procedure (SOP) "Identification, Handling, and Documentation of Protocol Deviations" (SOP-G-CL-0044). The number and percentage of participants with specific protocol deviations will be summarized for all enrolled participants by important and nonimportant deviations. To ensure completeness of the list of protocol deviations, the following will be verified programmatically from the database:

- 1. Participants from whom informed consent was not obtained
- 2. Participants who violated any IC/EC
- 3. Participants who received any disallowed medication or underwent any disallowed therapeutic procedure
- 4. Participants randomized to the ravulizumab treatment group who did not receive all of the planned number of infusions during the 26-week randomized Treatment Period

Protocol deviations from monitoring reports and other relevant sources will also be reviewed, and any important deviations will be included in the list that is summarized and reported.

Summary statistics will be presented by treatment group and overall.

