7.3. Efficacy Analyses

The mITT Set is the primary analysis set for all efficacy analyses. The primary analysis will be repeated on the PPS as supplementary analyses.

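### The disallowed-therapy criterion for the Per-Protocol Set is not limited to the 26-week endpoint window, so first use of a complement agent in follow-up removes a participant whose result is already settled

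*SAP*

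**What the plan says.** SAP 6.3 builds the PPS from mITT participants who meet four criteria. Criterion 1, receipt of the full randomized intervention, is expressly confined to the 26-week Treatment Period. Criterion 2 requires that participants "Did not receive any disallowed medications or undergo any disallowed therapeutic procedures as described in Protocol Section 6.6.2" and gives no period of its own. It lists three classes: experimental interventions, complement agents including eculizumab, and "Therapeutic plasma exchange/plasma infusion following randomization".

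Protocol 6.6.2, to which criterion 2 refers, sets two different windows:

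- For experimental therapies and complement agents: "Participants are prohibited from receiving any of the following medications and therapies during the entire duration of study participation".
- For plasma exchange or infusion: "Participants are prohibited from receiving therapeutic plasma exchange/plasma infusion at any time following randomization during the Treatment Period".

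On the use of the set, SAP 7.3 states: "The primary analysis will be repeated on the PPS as supplementary analyses". SAP 7.3.2 places all secondary analyses on the mITT Set. Under SAP 5.1, the primary endpoint, for participants without an intercurrent event, "will be assessed using all available assessments within the 26-week randomized Treatment Period".

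**The concern.** A per-protocol set normally asks whether a participant adhered over the period that produces the endpoint. Criterion 2 reaches past that period. Someone who received every dose, and whose response status is settled by Week 26, drops out of the PPS if a complement agent is first given in follow-up. That later treatment cannot have affected the result being estimated, so the PPS response rate is conditioned on an event after the endpoint.

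The SAP handles the same events differently for the mITT analysis. SAP 7.1.1 makes a participant a nonresponder for "initiation of disallowed therapy or medicine, before observing the response for an endpoint in analysis". Criterion 2 has no such tie to the endpoint.

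A second effect comes from early termination. SAP 4 says the study ends once the last participant in treatment completes Week 26. Time at risk of a follow-up exclusion therefore runs from none for that participant to as much as 26 weeks for early enrollees, so PPS membership depends partly on enrollment date.

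**Working it through.** The plan gives no figure on this point, so the check is mainly one of text, followed by an illustration of size.

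**Text**

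1. *Window of criterion 2.* Its own wording has no end date. The cross-reference supplies one for complement agents and experimental therapies: the end of study participation. SAP 4 and Protocol 4.1 include a 26-week Post-treatment Follow-up Period in the study, so the window can run to Week 52.
2. *Window of the endpoint.* SAP 5.1 and 7.3.1 confine Complete TMA Response to the 26-week Treatment Period.
3. *Use of the set.* SAP 6.3, 7.3 and 7.3.1 use the PPS only for that endpoint. No Week 52 analysis uses it.
4. *Anything that narrows criterion 2.* None was found. SAP 4.1 has a sentence limiting analyses to 26-week data, but it accompanies the planned primary analysis, which was cancelled. It also concerns the data analyzed, not membership of the PPS.
5. *Plasma exchange or infusion.* The SAP bullet drops the protocol's Treatment Period limit. Because criterion 2 also points to Protocol 6.6.2, that bullet is ambiguous for follow-up use; it does not clearly exclude it.

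Steps 1 to 3 together mean that first use of a complement agent or experimental therapy between Week 26 and the end of participation removes a participant from an analysis of data already complete at Week 26.

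**Size**

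Inputs: 16 enrolled (SAP 4) and 1:1 randomization. Assumed: n = 8 per arm, everyone otherwise in the PPS, and r responders in the arm. The documents give neither arm sizes nor responder counts. Intervals are Clopper-Pearson, the method SAP 7.3.2 names for binary secondary endpoints.

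Change in the arm's rate from one exclusion:

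- Responder removed: (r − 1)/7 − r/8 = (r − 8)/56
- Nonresponder removed: r/7 − r/8 = r/56

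With r = 5:

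| Case | Rate | Exact 95% CI |
|---|---|---|
| No exclusion | 5/8 = 62.5% | 24.5% to 91.5% |
| One responder removed | 4/7 = 57.1% | 18.4% to 90.1% |
| One nonresponder removed | 5/7 = 71.4% | 29.0% to 96.3% |

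The shifts are −3/56 = −5.4 points and +5/56 = +8.9 points. For r from 1 to 7, removing a responder moves the rate by −7/56 = −12.5 to −1/56 = −1.8 points. Removing a nonresponder moves it by +1/56 = +1.8 to +7/56 = +12.5 points.

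For a general arm size n, the largest shift from one exclusion is 1/n: setting r = n − 1 in r/(n(n − 1)) gives 1/n, and removing the only responder gives −1/n. A PPS arm smaller than 8 would therefore allow a larger shift, for example 1/5 = 20 points at n = 5.

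**The case against.** The strongest reply is that a Week 26 cut-off does not remove the conditioning. The endpoint is response at any time in 26 weeks, so a participant who responds at Week 4 has a settled result then. Such a participant would still be excluded for missing the Day 127 dose under criterion 1, or for eculizumab at Week 20 under an amended criterion 2. That is correct. The change aligns adherence with the endpoint window, which is ordinary per-protocol practice; it does not make the PPS free of events that follow response.

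A second reply is that excluding people who broke a standing prohibition is what a per-protocol set is for. Protocol 9.4.1 also foresaw selected secondary analyses on this set, some of which could have run to Week 52. That may explain the wide window. It does not justify it now that the SAP uses the set for the 26-week endpoint alone.

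Third, few participants can be affected. Those who stopped study drug already fail criterion 1. Protocol 4.1 provides for best supportive care on relapse, so a complement agent would be a deviation. The documents give no rate for such use and no sign that it occurred. This stands, and it limits the importance of the point. The event is still plausible: study drug stops at the end of the Treatment Period (Protocol 6.8), and TMA Relapse in follow-up is defined by a need for treatment (Protocol 3.2.5). Relapse is defined only for complete responders, so that route would remove responders, but nonresponders could be treated too.

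Finally, 8 per arm is all 16 enrolled and not a PPS count. The figures above are an illustration and not a bound.

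**Conclusion.** The concern holds, as a minor one. As written, criterion 2 selects participants on events that cannot affect the endpoint the PPS is used for, and nothing else in the SAP narrows it. The net direction is undetermined. Under the stated assumptions, one exclusion shifts an arm's rate by between 1.8 and 12.5 points in either direction, which is small against intervals some 67 to 72 points wide (91.5 − 24.5 = 67.0; 90.1 − 18.4 = 71.7).

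No decision turns on it. SAP 4.2 removes hypothesis tests and treatment comparisons, the PPS analysis is supplementary, and the mITT analysis does not change. Confidence is high about what the text says. Whether any participant is affected cannot be told from the documents.

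**What to change.** Give criterion 2 an end date, for example: *no prohibited medication or procedure received between randomization and the close of the 26-week Treatment Period*. Add the same Treatment Period limit to the plasma exchange/infusion bullet so that it matches Protocol 6.6.2.

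Report prohibited therapy in follow-up as a protocol deviation only. SAP 7.2.2, item 3, already covers this without a time limit: "Participants who received any disallowed medication or underwent any disallowed therapeutic procedure".

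The cost is one sentence in the SAP and a date condition in the PPS flag. No information is lost.

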6.4. Safety Set

The Safety Set will include all participants who receive at least 1 dose of study drug. Participants will be analyzed according to the study treatment they actually received. For a participant to be analyzed according to the treatment they actually received and not according to the randomization schedule, they would have to receive that treatment for all their study drug exposure visits. All safety analyses will be performed on the Safety Set.

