### 9.3. Populations for Analyses

The population sets used for analysis are defined in the following:

Population	Description
Intent to Treat	All randomized participants
Modified Intent to Treat (mITT)	All randomized participants, excluding participants who enroll prior to availability of ST-HUS and ADAMTS13 central laboratory results and are subsequently found to be ineligible after randomization
Safety Set	All participants who receive at least 1 dose of study drug. Participants will be analyzed according to the study drug they actually received for reporting exposure and safety data
Pharmacokinetic/Pharmacodynamic (PK/PD) Analysis Set	All participants who receive at least 1 dose of study drug and who have evaluable PK/PD data
Per Protocol (PP) Set	To be defined in the Statistical Analysis Plan

Abbreviations: ADAMTS13 = a disintegrin and metalloproteinase with a thrombospondin type 1 motif, member 13; ST-HUS = Shiga toxin-related hemolytic uremic syndrome

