#### **10.6.2.1. Guidance for Female Participants**

Female participants of childbearing potential must have a negative serum pregnancy test as required by local regulations within 2 weeks prior to the first dose of study drug and have a negative urine pregnancy test prior to the first dose of study drug on Day 1. Additional requirements for pregnancy testing during and after dosing with study drug are indicated in the Schedule of Activities (Section 1.3).

The Investigator is responsible for the review of medical history, menstrual history, and recent sexual activity to decrease the risk for inclusion of a woman with an early undetected pregnancy.

The Investigator should evaluate the potential for contraceptive method in relationship to the first dose of study drug.

Female participants of childbearing potential must use a highly effective or acceptable method of contraception, including at least 1 of the following until at least 8 months (generally 5.5 terminal half-lives) after the final dose of study drug. Highly effective methods are:

1. Intrauterine device in place for at least 6 weeks prior to first dose of study drug.
2. Progestogen-only hormonal contraception associated with inhibition of ovulation (either oral, injectable, or implantable) for at least 6 weeks prior to first dose of study drug.
3. Intrauterine progestogen releasing system for at least 6 weeks prior to first dose of study drug.
4. Bilateral tubal occlusion for at least 6 weeks prior to first dose of study drug.
5. Combined (estrogen- and progestogen-containing) hormonal contraception (either oral, intravaginal, or transdermal) for at least 6 weeks prior to first dose of study drug.
6. Surgical sterilization of the male partner (medical assessment of azoospermia is required if vasectomy was performed within the prior 6 months prior to the first dose of study drug). Male partner is still required to use condom during sexual intercourse.
7. Sexual abstinence for female participants:
  - Sexual abstinence is considered a highly effective method only if defined as refraining from heterosexual intercourse. In this study, abstinence is only acceptable if consistent with the participant's preferred and usual lifestyle. Abstinent female participants must refrain from heterosexual intercourse for at least 8 months after the final dose of study drug.

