6.5. Pharmacokinetic and Pharmacodynamic Analysis Set

All participants who receive at least 1 dose of ravulizumab and who have evaluable PK or pharmacodynamic (PD) data will be included in the PK/PD Analysis Set. PK and PD analyses will be performed on the PK/PD Analysis Set.

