7.7. Safety Analyses

All safety analyses will be conducted on the Safety Set and based on the actual treatment received. All safety data will be provided by treatment group, in participant listings. AEs will be coded in MedDRA and presented by MedDRA SOC and Preferred Term. No formal hypothesis testing is planned. Safety data will be presented separately for the 26-week randomized Treatment Period and Post-Treatment Follow-up Period.

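### SAP 6.4 would report a placebo-randomized participant who received some ravulizumab infusions under placebo in the safety summary tables, a narrowing of the as-treated principle that the SAP does not declare

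*SAP*

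**What the plan says.** Protocol 9.3 defines the Safety Set as everyone with at least one dose of study drug and adds: "Participants will be analyzed according to the study drug they actually received for reporting exposure and safety data". Protocol 9.4.2 repeats the principle for all safety analyses. Neither section attaches a condition or says what to do with someone who received both treatments.

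SAP 6.4 opens in the same way: "Participants will be analyzed according to the study treatment they actually received". Its next sentence restricts this. "For a participant to be analyzed according to the treatment they actually received and not according to the randomization schedule", it says, "they would have to receive that treatment for all their study drug exposure visits". Anyone who does not meet that condition stays in the randomized arm.

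SAP 7.7 goes back to unconditional wording: "All safety analyses will be conducted on the Safety Set and based on the actual treatment received". The list of changes from the protocol (SAP 4.2) and the SAP version history (SAP 4.3) do not mention the all-visits condition. No other section gives a rule for mixed exposure.

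**The concern.** An as-treated safety analysis is meant to count events in drug-exposed people under the drug. The SAP 6.4 condition does the reverse for one group: people randomized to placebo who were given ravulizumab at part of their infusions. Their adverse events, including any that began after a ravulizumab infusion, would be counted in the placebo column and its denominator. The same placement would carry into the other summaries made by treatment group on the Safety Set, such as infusions received, MACE rates and antidrug antibodies.

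The rule also works the other way: a ravulizumab-randomized participant with some placebo infusions stays under ravulizumab. That direction is harmless to the as-treated principle, because exposure to the drug did occur. With so few participants, one person in the wrong column is visible in every percentage.

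**Working it through.** The plan states no figure on this point, so there is none to reproduce. The check applies the rule to every possible dosing sequence and then sizes one participant.

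**Inputs**
- Planned dosing visits: Day 1 (loading) and Days 15, 71 and 127 (maintenance), from Protocol Table 7. Total 1 + 3 = 4.
- Classification rule: SAP 6.4, as quoted.
- Enrolled: 16 (SAP section 4). Randomization was planned 1:1, but the actual split and the number dosed are not given.

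**Step 1. Sequences for a placebo-randomized participant with all 4 infusions.** Each infusion is placebo or ravulizumab, so there are 2^4 = 16 sequences. Two are pure (all placebo, all ravulizumab), leaving 16 − 2 = 14 mixed.

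| Ravulizumab infusions out of 4 | Sequences | Group under SAP 6.4 | Group if any dose counts |
|---|---|---|---|
| 0 | 1 | Placebo | Placebo |
| 1 | 4 | Placebo | Ravulizumab |
| 2 | 6 | Placebo | Ravulizumab |
| 3 | 4 | Placebo | Ravulizumab |
| 4 | 1 | Ravulizumab | Ravulizumab |

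The two rules differ for 4 + 6 + 4 = 14 sequences, which are all the mixed ones. Even 3 ravulizumab infusions out of 4 leave the participant under placebo. These are counts of possible patterns and say nothing about how likely any of them is.

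The condition refers to the participant's own dosing visits. Someone who stopped early after receiving only the wrong treatment would be moved.

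**Step 2. Weight of one participant.** One person in an arm of n contributes 1/n to a percentage. The arm size is an assumption:
- n = 6: 1/6 = 16.7%
- n = 8: 1/8 = 12.5%
- n = 10: 1/10 = 10.0%

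**Step 3. The texts side by side.** Protocol 9.3, Protocol 9.4.2, the first sentence on treatment in SAP 6.4, and SAP 7.7 all say as treated, with no condition. Only the following sentence of SAP 6.4 restricts it. A programmer following SAP 6.4 exactly and one following SAP 7.7 alone could place the same mixed-exposure participant in different columns.

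**Step 4. Would the planned checks flag a case?** The programmed infusion check in SAP 7.2.2 (item 4) is limited to ravulizumab-randomized participants who missed planned infusions. It does not name placebo participants given ravulizumab. Detection would rest mainly on the review of monitoring reports and other sources described in the same section.

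**The case against.** The best defense is that the protocol leaves mixed exposure open. Treatment actually received does not settle where someone who received both belongs. Protocol 9.4 says the SAP will elaborate the methods, and SAP 6.4 does so by fixing a tie-break in advance. This stands in part: no text in either document sets an any-dose standard. But the tie-break chosen sends drug-exposed people to placebo, which is the case an as-treated analysis is meant to avoid, and the SAP does not present it as a change.

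Second, an any-dose rule has its own bias. A participant given placebo on Days 1, 15 and 71 and ravulizumab only on Day 127 would have every event from Day 1 counted under ravulizumab. This stands, and is why the fix shows event timing.

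Third, the situation is hypothetical. Allocation is central through IRT (Protocol 6.3.1), dosing is supervised and recorded (Protocol 6.4), and no misdosing is reported. This stands.

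A reader might also draw three stronger conclusions that the documents do not support:
- *That a drug-related serious infection would be concealed.* SAP 7.7 and 7.7.2 provide by-participant listings, and SAP 7.7.2.5 lists deaths and events of special interest, including meningococcal infections. With 16 participants these can be read line by line. The listings do not correct the tables, but the event would be seen. No safety hypothesis test is planned, so no formal decision depends on the column.
- *That the protocol itself counts one dose as 8 months of exposure.* The text "at least 8 months (generally 5.5 terminal half-lives) after the final dose of study drug" in Protocol 10.6.2.1 is contraception guidance. It does not say which arm owns an event.
- *That SAP 6.5 contradicts SAP 6.4.* The PK/PD Set takes "All participants who receive at least 1 dose of ravulizumab and who have evaluable PK or pharmacodynamic (PD) data". Membership therefore also needs evaluable data, the set serves another purpose, and it gives no group label for the safety tables. The contrast is awkward but is not a contradiction.

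**Conclusion.** The point holds as a limited one. Followed exactly, SAP 6.4 places every mixed-exposure participant randomized to placebo in the placebo safety column. This narrows the unconditional as-treated wording in Protocol 9.3 and 9.4.2 and SAP 7.7, and SAP 4.2 and 4.3 do not declare it.

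It is a weakness in a stated rule, not a shown error in results. If no mixed dosing occurred, no table is affected. If one case occurred, the effect is on summary tables only, at about 10 to 17 percentage points for one participant. That range assumes 6 to 10 participants per arm, because the documents give only the total of 16. Nothing in the documents allows an estimate of how often misallocation would happen. The priority is low, and the case for acting is that the correction costs almost nothing.

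**What to change.** In SAP 6.4, replace the all-visits condition with a sentence stating that, for safety summaries, any participant who received at least one dose of ravulizumab is summarized under ravulizumab. Add a footnote to the safety tables that identifies mixed-exposure participants and shows, for each of their events, whether it began before or after the first ravulizumab dose. If the sponsor prefers to keep the present condition, list it in SAP 4.2 as a departure from Protocol 9.3 and 9.4.2 and align SAP 7.7 with it.

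The cost is one sentence and one footnote, with no effect on study conduct and no change to any table if no mixed exposure occurred. The downside is that, in the main tables, a mixed participant's events from before the first ravulizumab dose count under ravulizumab. The footnote lets a reader separate them.
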